#### 5. Tertiary (exploratory) outcomes

- Development of end-stage renal disease within one year following angiography defined by the requirement for chronic dialysis for  $\geq 3$  months based on documentation in the United States Renal Data System database.
- Death within one year following angiography based on documentation in the VA Beneficiary Identification and Records Locator System, the National Center for Health Statistics National Death Index database, the Social Security Administration’s Death Master File and/or other similar databases.

## **H. Data collection**

### **1. Assessment of baseline demographic and clinical characteristics**

Following patient enrollment, research personnel will interview the subject and/or conduct a comprehensive review of the electronic medical record to abstract the following data elements:

- Whether the subject was an inpatient or outpatient immediately prior to the angiography procedure
- Demographic characteristics including date of birth, gender, race, and ethnicity
- Contact information including home, work, and cell phone numbers; address; email; preferred contact times; as well as the same information for an alternate contact
- Social security number
- Military history
- Pre-procedure laboratory parameters obtained as part of routine clinical care including date of test:
  - Hemoglobin level, serum glucose, serum bicarbonate, sodium, potassium and blood urea nitrogen most proximate to and within the 30 days preceding the index angiogram
  - If diabetic, most recent Hgb A1C within the past year
- Comorbid medical conditions including a history of :
  - Myocardial infarction, congestive heart failure, peripheral vascular disease, cerebrovascular disease, and chronic pulmonary disease. Standard procedures and definitions will be developed to systematically evaluate patients’ records for each of these conditions.
- History of hypertension or being prescribed blood pressure medication
- Smoking history
- Administration of any non-study IV fluid including the type within the 12 hours prior to the initiation of study IV fluids
- Weight in kilograms. The preferred method of obtaining the patient’s weight will be for research personnel to weigh them. In the event this is not possible, the most recent measurement found in the patient’s medical record will be recorded. Though not preferred, if there is no measurement in the medical record, this information will be collected via subject report.

- Blood pressure most proximate to and within 72 hours prior to the index angiogram including date of assessment
- Names of all pre-procedure medications, including those prescribed by physicians outside the VA, regularly taken by the subject
- Whether the subject was instructed by their physician to discontinue any medications before their angiography procedure and if so, the name of the medication.

## 2. Collection of baseline blood and urine specimens

Prior to the initiation of study IV fluids, the subject will be asked to provide a blood sample for Scr testing at the designated Central Laboratory. We will collect the date of this blood draw and whether it was collected prior to the initiation of study IV fluids.

In addition to the blood draw, subjects will be asked to provide a urine sample to measure urine albumin and creatinine. In the event the patient cannot provide urine prior to the angiogram, they will be asked to provide a urine specimen after the angiogram.

## 3. Evaluation of procedure-related data

Subsequent to the angiogram, research personnel will review the electronic medical record and angiogram procedure report to determine:

- Date of index angiogram
- Type of angiography
- Indication for coronary angiography
- Type and total volume of contrast administered. If ioxaglate (Hexabrix) or iohexol (Omnipaque) are noted, a reason must be given as to why that particular agent was used.
- Site of the arterial puncture for the angiogram
- Performance of percutaneous intervention
- Left ventricular end-diastolic pressure if measured
- Complications during the procedure including:
  - hypotension necessitating the administration of additional non-study IV fluid including the type of non-study IV fluid administered
  - hypotension necessitating the insertion of an intra-aortic balloon pump and/or the administration of vasopressor therapy
  - acute pulmonary edema necessitating the administration of IV diuretics

Assessment of procedure-related complications will ensure that we capture all events that could impact the development of our primary and secondary outcomes. To clarify and confirm all of these procedure-related data, research personnel may also conduct a brief structured interview with the angiography nurse/technician.

4. Evaluation of study IV fluid and NAC/placebo administration

Research personnel will track and record from the electronic medical record the total volume and total duration of study IV fluid administered pre-procedure, intra-procedure, and post-procedure, and the administration of NAC or placebo capsules while the patient is in the hospital. NAC or placebo capsule administration outside the hospital will be captured during a follow up assessment 5-8 days following the angiography procedure (See Section VII.H.8.).

5. Evaluation of post-procedure course (within 12 hours post procedure)

Research personnel will review the electronic record and collect the following data elements:

- Use of any IV fluids other than those specified as study IV fluids within the 12 hours following angiography including the type
- Use of IV inotropes, vasodilators, and/or vasopressors
- Episodes of hypotension defined as systolic blood pressure <90 mmHg and/or MAP <55 mmHg
- Performance of additional radiology procedures including coronary or non-coronary angiography or computed tomography with intravascular iodinated contrast including whether the procedure was planned and the type and volume of contrast administered

Within approximately four hours of the angiography, research personnel will obtain a urine sample from the patient and record the date of collection, whether study IV fluids were being administered at the time of collection and the urine pH value. The collection of this urine sample outside the range of 12 hours pre- and 12 hours post-angiography will constitute a reportable protocol deviation.

6. Evaluation of post-procedure hospitalization course (12 hours – 4 days post procedure)

Research personnel will review the electronic record on a daily basis for patients who remain in the hospital following their angiography procedure or for patients who are readmitted to the

hospital within 4 days of their angiography procedure to assess a series of events/procedures that could impact the risk for our primary and secondary outcomes. These include:

- Episodes of hypotension defined as systolic blood pressure <90 mmHg and/or MAP <55 mmHg
- Use of IV inotropes, vasodilators, and/or vasopressors
- Performance of additional radiology procedures including coronary or non-coronary angiography or computed tomography with intravascular iodinated contrast including the date of procedure, whether the procedure was planned and the type and volume of contrast administered. If ioxaglate (Hexabrix) or iohexol (Omnipaque) are noted, a reason must be given as to why that particular agent was used.
- Performance of surgical procedures requiring general or epidural anesthesia including the date and type
- Use of renal replacement therapy
- Occurrence of MI including the date and if it was an ST elevation MI
- Duration of hospital stay beginning at the time of angiography
- In-hospital death
- Date of hospital discharge

To capture these data in patients discharged from the hospital within the first 4 days following the index angiogram, we will provide patients with a study card at the time of their discharge with instructions to call research personnel if they visit an emergency room and/or are hospitalized within the 96-hour time frame following the index angiogram. For patients who visit a VA emergency room and/or are hospitalized within the VA, research personnel will review the electronic medical record to abstract the aforementioned data elements. For patients who visit a non-VA emergency room and/or are hospitalized outside the VA, research personnel will obtain the requisite release of information form(s) from the patient. Once the completed form(s) are received, research personnel will request the emergency room and/or hospital records to assess the aforementioned data elements.

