| Demographics  |                           | X h    |                                       |                                    |                         |                           |                             |                          |                         |
| Medical comorbidities   |                           | X h    |                                       |                                    |                         |                           |                             |                          |                         |
| Non-study IV fluid administration                                     |                           | X                 | X                                     |                                    |                         |                           |                             |                          |                         |
| Urine pH  |                           |                   | X                                     |                                    |                         |                           |                             |                          |                         |
| Procedural data/complications   |                           |                   | X                                     |                                    |                         |                           |                             |                          |                         |
| Post-angiography events   |                           |                   | X                                     | X e                     |                         |                           |                             |                          |                         |
| NAC pill count  |                           |                   |                                       |                                    |                         | X                         |                             |                          |                         |
| Assessment of adverse events  |                           | X                 | X                                     | X                                  | X                       | X                         | X                           | X                        |                         |

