## **B. Risks and benefits**

Any procedure/intervention has potential risks. The interventions used in this study may cause all, some, or none of the risks and side effects listed. There is also the potential for rare or unknown risks to occur. Active study participants will be informed of any information that becomes known during the course of the study regarding risks of the interventions that might affect their willingness to continue to participate.

1. Side effects associated with infusion of intravenous fluids

Reactions due to solution or technique of administration: febrile response, infection at the site of injection, venous thrombosis or phlebitis extending from the site of injection, and extravasation of fluids

2. Side effects associated with infusion of sodium chloride

Cardiovascular: heart failure (aggravated), edema

Endocrine and metabolic: hypernatremia, hyperosmolarity, hypokalemia, metabolic acidosis

Respiratory: pulmonary edema

3. Side effects associated with infusion of sodium bicarbonate

Cardiovascular: heart failure (aggravated), edema

Central nervous system: hyper-irritability or tetany may occur due to rapid shifts of free ionized calcium or serum protein alterations arising from changes in pH

Endocrine and metabolic: hypernatremia, hyperosmolarity, hypocalcemia, hypokalemia, increased affinity of hemoglobin for oxygen, reduced pH in myocardial tissue, necrosis when extravasated, intracranial acidosis, metabolic alkalosis

Respiratory: pulmonary edema

4. Side effects of NAC

Cardiovascular: flushing, tachycardia, edema

Dermatologic: urticaria, rash, pruritus

Gastrointestinal: diarrhea, nausea, vomiting

Respiratory: pharyngitis, rhinorrhea, rhonchi, throat tightness

Central nervous system: dizziness

<1%, postmarketing, and/or case reports (limited to important or life-threatening):

anaphylaxis, bronchospasm, chest tightness, cough, dyspnea, hypotension, respiratory distress, stridor, wheezing

Possible benefits of this study include a reduced risk of serious adverse outcomes, including death, need for acute dialysis, and persistent decline in kidney function among subjects receiving bicarbonate and/or NAC.

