### 1. Adverse events

Adverse events (AEs) are defined by the VHA Handbook 1058.01, paragraph 4 (a) as "An AE is any untoward physical or psychological occurrence in a human subject participating in research. An AE can be an unfavorable and unintended event, including an abnormal laboratory finding, symptom, or disease associated with the research or the use of a medical investigational test article. An AE does not necessarily have to have a causal relationship with the research. "

For the purpose of CSP 578, the study interventions are study IV fluids and oral NAC/placebo. Related events involve an assessment of the degree of causality (attribution) between the study interventions and the event. Site investigators will be asked to provide an assessment of

relatedness. All AEs with a reasonable causal relationship to the investigative treatment will be considered "related." A definite relationship does not need to be established.

Local site investigators, with assistance from their study coordinator, are responsible for collecting AE information regarding the subjects at their sites. During the study, data on adverse events will be collected spontaneously through patient reports, actively elicited during the angiography visit through open-ended questioning and examination, and gathered at the time of telephone contact and medical record reviews during the follow-up period. Related adverse event data will be collected from the time of consent to 35 days post angiography. If a patient receives care at a non-VA facility for an adverse event they experience, research personnel will obtain the requisite release of information form(s) from the patient and once received, acquire the pertinent medical records from the facility.

AEs related to the study intervention that are reported to research personnel will be recorded on an adverse event form and documented in source records (e.g., the electronic VA medical record and/or the subject's study record). In this way, the site creates a permanent record that provides information on the subject's clinical course while in the study.

Adverse events which develop into Serious Adverse Events, as defined below, will be reported as such and followed to resolution or stabilization.

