## 2. Serious adverse events

Serious adverse events (SAEs) are a subset of adverse events defined in VHA Handbook 1058.01, paragraph 4(r) and 21 CFR 312.32(a), as follows:

**Definition of SAE from CFR 312.32 (a):** Serious adverse event. An adverse event or suspected adverse reaction is considered "serious" if, in the view of either the investigator or sponsor, it results in any of the following outcomes: Death, a life-threatening adverse event, inpatient hospitalization or prolongation of existing hospitalization, a persistent or significant incapacity or substantial disruption of the ability to conduct normal life functions, or a congenital anomaly/birth defect. Important medical events that may not result in death, be life-threatening,

or require hospitalization may be considered serious when, based upon appropriate medical judgment, they may jeopardize the patient or subject and may require medical or surgical intervention to prevent one of the outcomes listed in this definition.

**Definition of SAE according to VA Handbook 1058.01:** An SAE is an untoward occurrence in human research that results in death, a life-threatening experience, inpatient hospitalization, prolongation of hospitalization, persistent or significant disability or incapacity, congenital anomaly, or birth defect, or that requires medical, surgical, behavioral, social, or other intervention to prevent such an outcome.

All SAEs, as defined in VHA Handbook 1058.01, paragraph 4(r) and 21 CFR 312.32(a), will be collected, regardless of whether or not they are considered related to the study interventions. SAEs with a reasonable causal relationship to the study interventions and associated medications will be reported as "related." A definite causal relationship does not need to be established.

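### Acute pulmonary edema needing IV diuretics is a named data item only during the procedure, so capture of non-serious edema in the other fluid phases is uneven and depends on attribution

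*Protocol*

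**What the plan says.** Protocol XII.B gives the same entry, "Respiratory: pulmonary edema", under both sodium chloride and sodium bicarbonate. Protocol VII.H.3 asks research staff to record complications during the procedure, among them "acute pulmonary edema necessitating the administration of IV diuretics", and explains: "Assessment of procedure-related complications will ensure that we capture all events that could impact the development of our primary and secondary outcomes". Protocol VII.H.6 describes its 12-hour to 4-day review as covering "a series of events/procedures that could impact the risk for our primary and secondary outcomes", but its list has no edema or diuretic item.

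Protocol VII.D.1 lets study fluid run for up to 12 hours on each side of the procedure. Protocol VIII.C.2 expects that some patients will develop overload or a raised left ventricular end-diastolic pressure during angiography, and that post-procedure fluid may then be stopped.

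For general safety capture, Table 6 schedules "Assessment of adverse events" from before angiography through day 90. Under Protocol XVI.B.1, events are "actively elicited during the angiography visit through open-ended questioning and examination", and also found by patient report, telephone contact and record review. The recording rule for non-serious events is limited by attribution: "AEs related to the study intervention that are reported to research personnel will be recorded on an adverse event form". Serious events, by contrast, "will be collected, regardless of whether or not they are considered related to the study interventions" (Protocol XVI.B.2).

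**The concern.** This trial compares two intravenous fluids in patients with kidney disease, including patients with non-decompensated heart failure. Acute pulmonary edema is an obvious harm to compare between the fluids. The protocol has a clear, objective item for it, tied to treatment given, but applies that item only in the procedure room.

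The same clinical event is therefore handled differently according to when it occurs. During the procedure it is recorded whatever its cause. During the pre- or post-procedure infusion, a non-serious episode reaches the adverse event form only if someone elicits it and the investigator judges it related to study treatment. At stake are the completeness and uniformity of one part of the fluid-safety comparison. An event that was never recorded cannot be recovered at analysis.

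**Working it through.** The plan states no figure to reproduce, so the check is a comparison of the data-collection lists in Protocol VII.H, with hypotension as the comparator.

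| Phase | List | Edema or IV diuretic item | Hypotension item |
|---|---|---|---|
| Before the procedure | VII.H.1 | none | none |
| During the procedure | VII.H.3 | one | yes |
| Within 12 hours after | VII.H.5 | none | yes |
| 12 hours to 4 days | VII.H.6 | none | yes |

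Hypotension, another event that could influence outcomes, is carried into both post-procedure reviews. Edema is not, although VII.H.3 and VII.H.6 give much the same reason for collecting their items.

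**Exposure outside the prompted window.** Protocol VII.D.1 sets minimum volumes of 3 mL/kg before and 6 mL/kg after, and a rate of 1 to 1.5 mL/kg per hour during the procedure. SAP Table 3 caps the pre- and post-procedure volumes at 12 mL/kg each.

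- Minimum volume outside: 3 + 6 = 9 mL/kg. At 1.5 mL/kg per hour, the procedure would have to last 9/1.5 = 6 hours to match it.
- Maximum volume outside: 12 + 12 = 24 mL/kg, which needs 24/1.5 = 16 hours.
- The documents give no procedure length. If 0.5 to 2 hours is assumed, the share given during the procedure runs from 0.5 × 1/(24 + 0.5) = 2.0% to 2 × 1.5/(9 + 2 × 1.5) = 25.0%. So 75% to 98% of the fluid is given outside it.

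This describes exposure only. Share of fluid is not share of risk, and these percentages do not measure missed events.

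**What already captures edema outside the procedure.**

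1. All serious adverse events, related or not (Protocol XVI.B.2). The VA definition there includes events that prolong hospitalization or need medical intervention to prevent a serious outcome. Edema treated with IV diuretics will often qualify.
2. Non-serious events judged related (Protocol XVI.B.1). A reasonable causal link is enough, and edema is a listed effect of both fluids.
3. A heart-failure discharge diagnosis within 90 days, index stay included (Protocol VII.G.4).
4. The general Table 6 rows for medications and post-angiography events. The SAP's list of monitoring-committee tables includes B9 (non-study drugs before and after the procedure), C1 and C2 (post-procedure assessment), and D4 and D5 (non-serious and serious events by organ class and preferred term).

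**What remains.** Two tests decide whether an episode outside the procedure is recorded as an adverse event: is it serious, and if not, is it judged related? Under the protocol's wording, an episode that fails both is not put on the form. A related but milder episode may also go unreported without a specific prompt. SAP 3.9 treats relatedness as a field and summarizes all non-serious events without repeating the related-only limit, so the gap is smaller if sites follow the SAP.

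**The case against.** The strongest reply is that what remains is close to empty. Acute edema that needs IV diuretics is often serious by the VA definition, and soon after a fluid infusion it will seldom be called unrelated. Most such events should reach the database. The overload scenario in Protocol VIII.C.2 also begins during angiography, inside the prompted window. The VII.H.3 item is collected because it may influence outcomes, not as a fluid-safety endpoint, and no stated objective compares edema between fluids. Finally, the case report forms, source worksheets, Operations Manual and current monitoring-committee table shells are not among the documents, and may already hold the item.

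Most of this stands, and it limits the point to a minor one. It does not remove it. In patients with known heart failure, a blinded investigator could reasonably attribute a short, treated episode to the underlying disease. The general rows may show that a diuretic was given without identifying edema as the reason. A discharge diagnosis does not place the event relative to the infusion.

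Three stronger readings are tempting and are not supported.

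- A reader might infer that edema outside the procedure goes unrecorded. The four routes above contradict that.
- A reader might infer bias between the fluid arms. The fluids are blinded and share one volume schedule, volumes and durations are to be monitored across groups (Protocol VIII.C.1), and nothing shows that capture would differ by arm.
- A reader might infer that the reason for stopping fluid early is not collected. No such field is described, but that is silence about forms not seen. A volume below the minimum is in any case prohibited (Protocol VII.D.1), so it should produce a deviation form whose justification is reviewed (Protocol XIV.C).

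**Conclusion.** The point holds as a minor weakness in data collection. There is one named edema item across four phases, and it covers only the procedure itself. The consequence is limited to uneven, attribution-dependent capture of non-serious edema during the pre-procedure infusion and after the procedure.

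The primary analysis, sample size and type I error are unaffected. The size of the loss cannot be estimated: the documents give no edema rate, no proportion judged unrelated and no capture rate. A reader might infer a substantial loss of power for the fluid-safety comparison. That would require a large fraction of all edema to be missed, which the documents do not suggest.

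The conclusion rests on Protocol VII.H being a fair account of what sites are prompted to record, and on sites following the protocol's related-only rule rather than the broader wording of SAP 3.9.

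**What to change.** Repeat the existing VII.H.3 item, unchanged and regardless of attribution, in three places: the pre-procedure infusion, the within-12-hours review (VII.H.5) and the 12-hour to 4-day review (VII.H.6). Report it by fluid arm in the monitoring-committee and final safety tables. If the case report forms already hold the item for these phases, naming it in VII.H is enough.

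A yes/no field for study fluid stopped early because of overload or raised left ventricular end-diastolic pressure, with the phase, would help in interpreting volume shortfalls, but it is optional.

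The post-procedure items fit record reviews that sites already perform, and the pre-procedure item can be abstracted from the same medical record. No new visit, test or consent change is needed. The downside is slight extra data entry and an added row in the safety tables.
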